Overall Design: This will be an extension study to the 2-year MAGNIFY MS trial (i.e., parent study) to observe participants in Year 3 and 4 after the 2-year treatment with cladribine tablets; no cladribine tablets will be administered during the extension study period. Participants will attend visits for assessments at extension study Baseline, which is planned to coincide with the last visit of the parent study at 12 months after initiation of the second year cladribine treatment (or 24 months after initiation of first year treatment if the participant did not initiate the second year treatment); for participants who complete the parent study before the recruitment is open for the extension study, the extension study Baseline visit may be planned later, after the parent study last visit and before Visit 1. For these patients, data will be collected retrospectively from the potential gap period between the parent study last visit and the extension study Baseline. In addition, participants will attend Visit 1 (at Month 12/Year 1 since parent study last visit) and Visit 2 (at Month 24/Year 2 since parent study last visit). The study includes 3 sub-studies, which include additional sample collection from participants who agree to participate.

Disclosure Statement: This will be an open label, single arm, exploratory, multicenter, 2-year, retrospective and prospective, Phase IV extension study. The primary purpose is the evaluation of long-term disease activity after treatment with cladribine tablets in adults with highly-active RMS. No cladribine tablets will be administered during the study, but the study has an interventional nature due to mandated visits and assessments (including MRIs and blood draws).

Number of Arms: 1.

Blinding: Not applicable.

Number of Participants: A maximum of 256 participants are planned to be enrolled to obtain 200 to 220 evaluable participants.

[figure not shown]
Study Intervention Groups and Duration: The extension study will cover a 2-year period in which the participants will not be administered cladribine tablets, which was administered during the parent study. Participants will be followed up for 2 years.

Involvement of Special Committee(s): Yes.

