1.3 Schedule of Activities

The order of the assessments is as provided in the Schedule of Activities (Schedule of Activities) (Table 2).

Table 2: Schedule of Activities

Assessments & Procedures Assessment Period					
	Extension Baseline	Visit 1	Early withdrawal / Visit 2	Unscheduled visits	Notes
Study month		12	24	Baseline Visit-24	
Visit window		± 30 days	± 30 days		
Informed consent	X				Informed consent should be obtained prior to any study-specific assessments.
Inclusion/exclusion criteria	X				Enrollment will be done after the confirmation of fulfilling all inclusion criteria without matching any exclusion criteria.
Demography	X				
Concomitant medications and procedures	X	X	X	X	Baseline: Collected retrospectively for potential gap period (see Section 4.1).
MRI					
Magnetic Resonance Imaging (MRI),		Х	Х		
Disability					
Disability: Expanded Disability Status Scale (EDSS)/	х	Х	Х	х	Baseline: Retrospective data collection of any EDSS performed during the potential gap period (see Section 4.1). Unscheduled visits: Required if relapse is suspected (see Section 4.1).
CCI					,
		X	х		
CCI		•	•		
		Х	Х		
Relapse reporting	х	х	Х	х	Baseline: Retrospective data collection for potential gap period (see Section 4.1). Unscheduled visits: Required if relapse is suspected (see Section 4.1).
Collection and review of patient diary		×	X	Х	To be captured into the respective electronic case report forms (eCRFs) from patient diary in case of any entry at home.
Safety Assessments					
Adverse event reporting	Х	X	X	Х	Also captured in patient diary when at home. Baseline: Collected retrospectively for potential gap period (see Section 4.1).

Assessments & Procedures	Assessment Period				
	Extension Baseline	Visit 1	Early withdrawal / Visit 2	Unscheduled visits	Notes
Study month		12	24	Baseline Visit-24	
Visit window		± 30 days	± 30 days		
Physical examination		Х	Х	X	
Vital signs		Х	Х	Х	
Medical history	Х				Only serious adverse events (SAEs) and lymphopenia (also if not serious) which are ongoing since the parent study (see Section 8.3.1)

Substance code: N/A MS700568_0157

Extension to the MAGNIFY MS trial on Mavenclad®

Assessments & Procedures	Assessment Period				
	Extension Baseline	Visit 1	Early withdrawal / Visit 2	Unscheduled visits	Notes
Study month		12	24	Baseline Visit-24	

\sim	
J	

CCI	CSF: Cerebrospinal fluid; DMD: Disease Modifying Drug; eCRF: Electronic Case Report Form; EDSS: Expanded Disability Status
Scale; CCI	
CCI	SAE: Serious Adverse Event; CC

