8.1.1.1 MRI Scanning Procedure

The MRI measures of white matter lesional activity (i.e. new/enlarging T2 lesions or Gd+ T1 lesions) and those of brain atrophy (i.e. the percentage of brain volume change) have shown to be valid surrogate endpoints for clinical outcomes.

Restrictions for the MRI schedule:

In order to prevent interferences caused by a DMD, steroid or adrenocorticotropic hormone (ACTH) administration or by relapse, the following restrictions will apply:

- For any relapse that may require a steroid or ACTH treatment, the MRI acquisition should be planned as scheduled and at least occurring after 30 days of the last dose of steroid/ACTH.
- For any relapse that may require a DMD treatment, if the scheduled MRI is in the next 30 days, acquire MRI in advance before initiation of DMD. If DMD already initiated without possibility to acquire MRI in advance, discuss each case with a Medical Monitor on how to handle the MRI acquisition.

All scans will be performed according to a standard protocol detailed in a separate Image Acquisition Guidelines document. Central imaging core lab will independently perform the analysis of all MRI scans to meet study endpoints. As with other laboratory tests and clinical measures, strict adherence to the MRI scanning protocol, and prompt handling of the scans is essential in obtaining a meaningful result.

Investigator should also ensure that the MRI scan is locally evaluated either by themselves/site radiologist for safety to rule out progressive multifocal leukoencephalopathy and/or any serious central nervous system disease (e.g., tumor, stroke etc.). For participants switching to other DMDs the safety/follow-up will be additionally assessed by the Investigator. Any unscheduled MRI acquired for such switching or for other safety reasons during the study will be analyzed by the Investigator/site radiologist as per standard of care.

Prior to participant assessment, each study site may be asked to send a 'test' or 'dummy-run' scan to assess image quality and shipment procedures, to evaluate the accessibility of the electronic data carrier, and to assess the ability to correctly reposition participants so as to get comparable brain images. Only upon final approval of this test scan, sites will be allowed to begin assessing participants.

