8.3.6 Disease-Related Events and/or Disease-Related Outcomes Not Qualifying as AEs or SAEs

The following disease-related events are common in participants with highly-active RMS and can be serious/life threatening:

• Symptoms and signs of relapse or worsening of MS

Because these events are typically associated with the disease under study, they will not be reported according to the standard process for expedited reporting of AEs and SAEs even though the event may meet the definition of an AE or SAE. These events will be recorded on the relapse module of the eCRF page within 15 days after the visit.

However, if either of the following conditions applies, then the event will be recorded and reported as an SAE (instead of a disease-related event):

• The event is, in the Investigator's opinion, of greater intensity, frequency, or duration than expected for the individual participant (i.e. worsening not consistent with the anticipated natural progression of the disease).

[figure not shown]
OR

• The Investigator considers that there is a reasonable possibility that the event was related to study intervention.

8.4	Treatment of Overdose
Not applicable.	
8.5	Pharmacokinetics
Not applicable.	
8.6	Pharmacodynamics
Not applicable.	
CCI	
001	
CCI	

8.9	Immunogenicity Assessments
Not applicable.	
rvot apprication.	
 	
0.4	
9.1	Statistical Hypotheses
No formal statistical	hypothesis will be tested, as the study is designed to be exploratory.
CCI	

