All statistical tests mentioned in this IAP are to be regarded as descriptive and exploratory, and differences with a p-value of 0.05 or less will be considered nominally statistically significant. No correction for multiple testing will be applied for any of the analyses. If confidence intervals (CI) are to be calculated, these will be two-sided with a confidence probability of 95%, unless otherwise specified in this IAP.

Study data will be integrated with study data from the MAGNIFY MS trial as required to perform the statistical analyses, i.e., study data up to M24 visit is integrated from the MAGNIFY MS trial.

If not specified otherwise, all listings will only include data collected in the Extension Study, including the gap period between the MAGNIFY MS trial and MAGNIFY MS Extension Study. Listings regarding demographic and other Baseline characteristics will include data from MAGNIFY MS Baseline.

If data from parent study are used, all rules from parent study IAP still apply for the analysis of these data, except alternative rules are explicitly specified in this IAP.

All analyses will be performed using SAS® Software version 9.4 or higher or R (http://www.r-project.org/), Version 3.6.3 or higher as applicable.

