9.5 Time Window

- Day 1 is the day of start of study medication at MAGNIFY MS Baseline Visit, the day before is Day -1 (no Day 0 is defined).
- Study day is defined relative to Day 1.

The visit schedule in the Extension Study is defined as follows:

- 1 month = 30 days,
- 1 year = 360 days,

relative to the M24 Visit in the parent study.

- MAGNIFY Extension Baseline Visit: The visit is planned to coincide with or be as near to M24 as possible to minimize the transition gap period, it may also be the same visit as M24.
- Visit 1: 1 year ((360 days) after M24 Visit (\pm 30 days)
- Visit 2: 2 years (720 days) after M24 Visit (± 30 days)

Visit 1 and Visit 2 will also be referred to as the M36 Visit and the M48 Visit, respectively, in the following sections of this IAP as well as in the Tables, Listings, and Figures (TLF) outputs, for consistent presentation of analyses and results over time. Footnotes will be added in the TLF outputs to clarify that these Visits are to be understood as nominal Visits.

In each analysis, should an assessment be delayed, participants' assessment data will be treated as though it occurred at the nominal time point specified (i.e., data collected out of visit windows will not be excluded or adjusted in any analysis) and inferences will be conducted accordingly. Thus, further time windows will not be specified. The MRI assessment will be the only exception to this rule. Handling of out-of-window MRI assessments is discussed in Section 9.8.

All observations from unscheduled visits will be included only in the analyses of visit independent summaries (e.g., counts of AEs, concomitant medications and procedures, relapse reporting and EDSS) unless for the last assessment available. In this case the missing Early Withdrawal (EW) visit will be imputed by the unscheduled visit.

The assessments of the EW visit will be mapped to the nearest planned post-baseline visit with a missing assessment before or after the EW visit of the individual assessment for all statistical analyses and descriptive summaries. As not all assessments of the EW are performed at each visit, the different assessments of the EW can be assigned to different visits. If the duration (in days) between the EW visits and two missing planned visits are equal, then the assessment will be assigned to the later visit.

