The 6MCDP during Extension Study Period is defined as sustained increase in EDSS score that started during the Period. A Sustained Increase in EDSS score is defined by an increase of:

- at least 1.5 points if the Baseline EDSS score was 0, or
- at least 1 point if Baseline EDSS score was between 0.5 and 4.5 inclusively, or
- at least 0.5 point if the Baseline EDSS score was at least 5,

that occurs over a 6-months' time-period.

The increase will be defined as sustained when it occurs on two post-Baseline Visits during the Extension Study Period that are at least 166 days apart (to be consistent with the parent study minimum visit gap) and no observations at any other visits (including unscheduled visits) in between are less than the defined increase. The assessment date of the earlier of the two EDSS assessments with the defined increase will be defined as the start date of 6MCDP.

For descriptive summaries the following rules will be defined:

Qualifying Relapse

- Yes: any qualifying relapse reported during the Extension Study Period,
- No: Extension study period completed, and no qualifying relapse reported during the Extension Study Period,
- Unknown: otherwise.

6MCDP

• Yes: sustained increase in EDSS score that started during the Extension Study Period,

- No: at least 2 post-Baseline EDSS assessments that are 166 (or more) apart and no sustained EDSS progression that started during the Extension Study Period,
- Unknown: Otherwise.

MRI activity

- Yes: any T1-Gd+ or active T2 observed during the Extension Study Period,
- No: at least one post-Baseline MRI and no T1-Gd+ or active T2 observed during the Extension Study Period,
- Unknown: otherwise.

Analysis (Analysis Set)	Derivation	Statistical Analysis Methods	Missing data handling		
	Primary endpoint: Proportion of participants with NEDA-3 during Year 3 Visit and Year 4 Visit Period after the initial dose of cladribine tablets				

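### The 6MCDP rule in SAP 14.1.1 has no relapse-free condition, so two transient relapse-related EDSS rises can be scored as sustained progression

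*SAP*

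**What the plan says.** **The rule.** SAP 14.1.1 calls an EDSS increase sustained when "it occurs on two post-Baseline Visits during the Extension Study Period that are at least 166 days apart" and "no observations at any other visits (including unscheduled visits) in between are less than the defined increase". The event is dated to the earlier of the two scores. No condition refers to relapse. Protocol 8.1.2.1, which uses 3-month confirmation, has none either.

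**Which scores count.** SAP 9.5 admits unscheduled observations to "visit independent summaries (e.g., counts of AEs, concomitant medications and procedures, relapse reporting and EDSS".

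**When EDSS is taken.** SAP 9.5 places Visit 1 and Visit 2 at 360 and 720 days after Month 24, each ±30 days. The EDSS row of the Protocol 1.3 schedule adds: "Unscheduled visits: Required if relapse is suspected (see Section 4.1". Protocol 8.1.3.2 asks for the examination no later than 7 days after the event is reported. Protocol 4.1 leaves any further assessment after a relapse to the physician, so no recovery EDSS is required.

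**Relapse elsewhere in the protocol.** For imaging, Protocol 8.1.1.1 sets timing rules: "In order to prevent interferences caused by a DMD, steroid or adrenocorticotropic hormone (ACTH) administration or by relapse, the following restrictions will apply". There is no counterpart for EDSS.

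**Where 6MCDP is used.** It is a component of NEDA-3 (14.1.1, 14.2.1), it appears in the crude component summaries (14.1.2, 14.2.1), and time to first 6MCDP is a secondary endpoint in its own right, from Day 1 and from Month 24 (14.2.3).

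**The concern.** A confirmation rule exists to separate lasting disability from the temporary worsening of a relapse. Here the scores most likely to fall between the yearly visits are those prompted by a suspected relapse. They tend to be high, because Protocol 8.1.3.1 makes a rise in a functional system score or in total EDSS part of the definition of a qualifying relapse. The score most likely to disprove a temporary rise, one taken after recovery, is the one that nobody has to take. A recovered score at Visit 2 does not help if it comes after the confirming score, because only values between the two scores can refute.

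At stake is the meaning of the separately reported 6MCDP results. If relapses can produce progression events, time to first 6MCDP partly measures relapse. A relapse-time score can also set too early a start date for a progression that is real.

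**Working it through.** The documents give no 6MCDP rate, and the protocol states that no formal statistical "hypothesis will be tested, as the study is designed to be exploratory", so there is no planned figure to reproduce. The check has four steps.

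**1. Can it happen?** Apply the rule to one participant:

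- Baseline EDSS is 2.0, so the threshold is 3.0 (at least 1 point for a baseline of 0.5 to 4.5).
- Visit 1 falls in a relapse: 3.0. Recovery is not measured.
- A second relapse comes about 270 days later, with an unscheduled EDSS of 3.5.
- Visit 2: 2.0.

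The two raised scores are more than 166 days apart with nothing between them. Visit 2 is later than both. Result: 6MCDP = Yes, dated at Visit 1, in a participant who is back at baseline.

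**2. How often does the visit schedule allow it?** Take two relapses at random times in the 720 days.

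- At least 166 days apart: (1 − 166/720)² = 59.2%.
- At least 166 days apart and between the same two scheduled visits: 0.5 × (1 − 166/360)² = 14.5%.
- Ratio: 14.5/59.2 = 24.5%.

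The other eligible pairs straddle Visit 1, where a recovered score blocks the event.

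**3. How many participants?** The rule was simulated with EDSS at days 360 and 720 and within 7 days of each relapse. Every rise was taken as fully transient. Three inputs are assumptions, not document figures: relapse rate, duration of the rise, and share of relapses reaching the threshold. The base of 220 is the upper figure in "A maximum of 256 participants are planned to be enrolled to obtain 200 to 220 evaluable participants". Expected false 6MCDP per 220:

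| Relapses per year | 30-day rise, half reach threshold | 30-day, all | 90-day, half | 90-day, all |
|---|---|---|---|---|
| 0.05 | 0.04 | 0.18 | 0.07 | 0.24 |
| 0.10 | 0.19 | 0.70 | 0.28 | 1.05 |
| 0.20 | 0.66 | 2.74 | 0.93 | 3.90 |
| 0.30 | 1.38 | 5.76 | 2.03 | 8.19 |

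Among participants with two relapses at least 166 days apart, about 29–48% are scored as 6MCDP if every relapse reaches the threshold, and about 7–12% if half do.

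Hand check at 0.10 per year: the mean number of relapses is 0.10 × 720/365.25 = 0.197, so P(two or more) = 1 − e^(−0.197) × 1.197 = 1.7%, or about 3.75 of 220. Of these, 3.75 × 0.592 = 2.2 have a pair far enough apart. Multiplying by the simulated shares at this rate (8.4% to 45.4%) gives 0.19 to 1.0, in line with the table.

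If a recovery EDSS existed about 120 days after each relapse (0.20 per year, 90-day rise, all reaching threshold), the false rate would drop from 1.8% to about 0.1%. The missing recovery score is therefore what drives the problem.

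**4. Does NEDA-3 move?** Its event date is the earliest of relapse onset, 6MCDP start and MRI activity. In every simulated scenario the false 6MCDP began on or after the first relapse onset, so NEDA-3 status and date changed in 0 cases. The simulation contains only qualifying relapses, so it cannot speak to one exception: a raised Visit 1 score with no qualifying relapse in the period, confirmed only by a relapse-time score in Year 4. That would date a failure at Visit 1 and turn a Year 3 NEDA-3 participant into a Year 3 failure.

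**The case against.** **The primary result is safe.** A reader might infer that NEDA-3 is biased. The documents do not support that: a qualifying relapse is itself a failure, dated at onset. The exception in step 4 is narrow. Protocol 8.1.3.2 postpones the examination while fever or infection cannot be excluded, and a symptomatic rise large enough for 6MCDP will usually also satisfy the relapse criterion on EDSS. This objection stands.

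**Confirmation is not automatic.** A reader might infer that two relapse rises are always scored. They are not: any lower score in between blocks the event, and most pairs straddle Visit 1. For participants with a gap period, EDSS from the gap and from Extension Baseline also count (Protocol 4.1, SAP 11.3) and can refute. This stands too.

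**A larger count does not hold.** A reader might note that, at 0.10 relapses per year, 0.10 × 194/365.25 = 5.3% (about 11 of 200) have a relapse in the 360 − 166 = 194 days that could confirm a Visit 1 score, and suppose that 10–20% of them are above threshold at Visit 1, giving 1 to 2 false events. The documents give no such percentage. With a 90-day rise, only 0.10 × 90/365.25 = 2.5% would be in relapse at Visit 1, so this route yields 200 × 5.3% × 2.5% = about 0.3.

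**Double counting.** The main descriptive table in 14.1.1 classifies by earliest event. The crude tables show components separately by design, so overlap there is not itself an error.

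**Wording.** It could be argued that the two confirming visits must be scheduled ones. The phrase that admits unscheduled visits as other visits, together with SAP 9.5, points the other way. Even on the narrow reading, the simulation leaves about 0.2–0.5% (relapse rates 0.20–0.30, 90-day rise, all reaching threshold).

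**Parent consistency.** SAP 7 adopts 6MCDP to match the parent study, and the parent analysis plan is not available here. It may hold a relapse rule for parent data, so the effect on the Day 1 endpoint cannot be sized. For the extension period, SAP 14.1.1 writes the definition out without one. The wish for consistency is a reason to report the current definition as well, not to leave the gap open.

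**Conclusion.** The gap is real: nothing in the SAP or protocol keeps a relapse-time EDSS from starting or confirming 6MCDP, and the schedule makes such scores the main observations between yearly visits. Two transient rises can be scored as sustained progression when no lower score separates them. The results affected are time to first 6MCDP, from Day 1 and from Month 24, and the crude 6MCDP summaries.

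The size is small: about 0.2 to 1 of 220 at 0.10 relapses per year, and about 8 of 220 only at the extreme corner of the table. These figures assume fully transient rises and no gap-period scores; the relapse rate, the duration of the rise and the share reaching threshold are not in the documents. The change is worth making because it is cheap and the endpoint is reported on its own, not because the primary estimate is in doubt.

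**What to change.** In SAP 14.1.1, carried into 14.2.1 and 14.2.3:

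- An EDSS obtained within 30 days after onset of a reported relapse may not confirm 6MCDP. Repeat with 90 days as a sensitivity analysis, since a longer rise could still be present when a scheduled visit falls more than 30 days after onset.
- Add a sensitivity analysis in which such a score may not set the 6MCDP start date either.
- Below-threshold scores continue to refute, whenever taken, and relapse-time scores are still used to qualify relapses.
- A participant with a threshold score whose only later EDSS falls inside the interval is classed as Unknown, not No, and listed. The present definition of No would otherwise absorb some of them.
- Report the current definition alongside, for consistency with the parent study.

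The cost is a few sentences and a date filter. Relapse onset and EDSS dates are already collected. The downside is that a few genuine progressions become unconfirmed because their only later score was close to a relapse; the listing makes them visible.
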